13.2.2. Secondary Outcomes

- (1) Patient satisfaction (rated after visits; self-report)
- (2) Missed opportunities for communication about sex (defined in the paragraph below)
- (3) Providers' barriers to communication about sexual health (self-report)⁶⁸
- (4) Two additional communication behaviors coded from audio recordings: (a) raising the topic of sexual health (clinician initiated the discussion) and (2) Raising the topic with counseling (e.g., "Many women on this treatment experience sexual concerns")

13.2.3. Analyses

Because there is no existing validated dialogue coding scheme for patient-provider discussions of sexual issues, the dialogue coding will be conducted largely through the generation of a new code book which will be able to be applied to subsequent data sets. Audio recorded dialogue will be coded using the following three methods, through N Vivo or similar software program that can be used to analyze verbal communication data, such as SPSS: 1) [name] will work with [name], a patient-provider interaction coding expert and mentor on the PI's MRSG, to develop a sexuality dialogue codebook. We will code physical sexual concerns as pertaining to performance of sex (e.g., lubrication, orgasm, discomfort), fertility-related concerns, and motivational/emotional concerns (e.g., desire, satisfaction, enjoyment, intimacy, body image, and femininity).^{9,19,28,36} 2) Frequency and quality of provider sexual communication behaviors (primary outcomes listed above) will be coded, as well as other provider and patient communication behaviors that are of interest (e.g., patient question asking), using qualitative methods to draw out behaviors from the dialogue data. We will also code "**missed opportunities**" for **communication about sex** based on (a) coding patient cues not pursued by providers⁸⁸ (e.g., "I wasn't told how this would affect my sexual function") or reporting of symptoms/side effects known to effect sexuality (e.g., menopausal symptoms) that could serve as a cue for providers to discuss sexual issues; and/or (b) considering patients who score > 0 on the PCM sexual concerns screening item but for whom sexual concerns are not discussed in their clinic visit, according to their self-report, a missed cue. 3) We may also code for discussions of other common patient complaints including pain and fatigue; these offer interesting comparators with sexual concerns in terms of the frequency and complexity of discussions. The dialogue will be coded in two stages, first for the presence of any discussions of sexual health (and related health issues), and secondarily, for the more detailed codes generated in the codebook. In order to develop the codebook mentioned above, [name] and [name] will analyze the baseline set of encounters until a codebook is generated, and [name] will apply these codes to the encounters. To ensure that discussions of sexual health are not missed, a trained coder will code a random 20% of the transcripts to ensure inter-rater reliability, unless two coders code all data. Regular meetings will be held to discuss definition changes and coding problems and to resolve any inconsistencies. We will consider inter-rater reliability of $\geq .60$ on our key outcomes to be adequate based on prior research.⁸⁹ Dialogue will be analyzed through transcripts of the audio recordings. A first analysis will characterize the communication at baseline (pre-provider training). The next set of analyses will concern the changes proposed through the intervention.

Descriptive analyses (e.g., frequencies, measures of central tendency) will determine the feasibility and acceptability of the training program. Seventy-five percent of participants rating the training program favorably ("Agree"/"Strongly

Agree" or "Satisfied"/"Very Satisfied") on study evaluations will be considered adequate acceptability. Patients at baseline and post-intervention will be compared on socio-demographic and medical variables using Chi-square tests or t-tests. Pilot efficacy analyses will be calculated through the following method. Mean differences will be calculated in self-report outcome measures at baseline and 6-month follow-up as the final endpoint, along with standard deviations and the effect size (mean difference/SD of the differences). Regarding the communication outcomes, if audio recordings are available, those data will be used. If there appear to be significant differences between the audio recorded and the self-report communication data, separate analyses may be conducted for these two types of data. Clinician communication outcomes will be examined descriptively by comparing the proportions of clinic visits in which the target communication behaviors occurred at post-intervention versus baseline. Additionally, we will conduct exploratory analyses on the communication variables where the effect of post-intervention was evaluated using generalized linear models with robust standard errors via Generalized Estimating Equations to account for within-provider correlation. Specifically, logistic regression will be used to examine binary outcomes, Poisson regression will be used to examine length of discussion about sexual health and a risk ratio presented for this variable (no discussion was coded as zero seconds), and ordinal logistic regression will be used to examine intervention effects on complexity of communication (categorized as 0, 1, or 2) and on patient satisfaction. Although the study was not powered for formal comparisons, we will consider presenting the model based estimates of effect sizes and corresponding 95% confidence intervals.

Additional analyses will concern the validation of the patient communication self-report measure that we have developed to supplement, and in some cases replace, the audio recorded dialogue obtained from clinic encounters. A major part of this analysis will be to examine how well the audio recorded and self-report communication outcome measures correlate using kappa calculations or other appropriate statistical tests for agreement.

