In Phase I, we anticipate enrolling 8 oncologists and 4 nurse practitioners (NPs) who treat breast cancer patients from Fox Chase/Temple affiliates or other sites to participate in qualitative interviews. If adequate qualitative information is not obtained from these interviews, additional interviews (a maximum of 6) may be held with oncologists/nurse practitioners until the data have reached "saturation" (i.e., no substantial new information is gained); alternatively, if saturation is reached with fewer provider interviews (no less than 6 oncologists and 3 NP's), we may consider stopping recruitment early for this phase. A target of four oncology fellows from FCCC (range of 3-8, depending on the adequacy of information received) will participate in the mock training. A new group of 6-8 Fox Chase/Temple or partner site breast cancer providers, consisting of oncologists and advanced practice clinicians, e.g., Nurse Practitioners, Physician Assistants, who agree to have clinic visits with enrolled patients analyzed will complete the pilot training program (Phase II). To establish a pattern of provider behavior, 8-16 patients per provider will be recruited for all phases of the clinic visit assessment study (Phases II and III; see study design figure in section 4.3), however, due to the unpredictable nature of clinic schedules, we may ultimately recruit fewer than 8 or more than 16 patients for some providers (e.g., we may recruit more heavily from some clinics if other clinics do not offer enough eligible patients). We leave open a fairly wide range for the number of total audio recorded clinic visits per clinician because the total number needed will depend on the data obtained on our target outcome variables and on the number of clinicians who participate; if very few conversations occur regarding sexual concerns, we may need to record more clinic encounters. In the case that a provider participant who has consented to audio recording shares their clinic encounters with fellows, nurses, students, or another third party, those fellows will also be consented using separate consent forms so that their involvement in each clinic visit included in the study can be audio recorded.

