For participating in Phase I (Qualitative Study) providers will receive \$75. Providers in Phase II (Provider Training) will receive \$500 to compensate them for the substantial time and efforts involved in allowing us to assess communication in multiple patient visits, participate in the provider training program, and complete follow-up materials. They will receive this compensation split between three time points, in order to allow for a more timely repayment of their efforts: providers will receive \$200 at the time of completion of post-intervention surveys, which will occur at the end of the provider training, another \$200 once all follow-up Phase II clinic encounters have been assessed (and recorded, if possible), and a final \$100 at the time of completion of the 6-month post-training survey. Fellows, nurses, students, or other third parties that are recorded as part of the clinic visit assessments will not be compensated. Providers participating in Phase III will be compensated \$25 after the audio recording of their first patient and an additional \$25 after the audio recording of their final patient (i.e., at the study conclusion), for a total of \$50. Compensation will be provided in the form of gift cards or check.

Number of subjects per year projected at FCCC	Total target accrual	Number of subjects nationally or internationally (if applicable)	Number of subjects at collaborating institutions (if applicable)
Up to: 59*	339	N/A	29*

* The yearly rate will differ by study phase. In Year 1, we anticipate enrolling up to 59 Fox Chase or Temple patient participants (though some participants may be from other outside sites) and 4 oncology fellows for Phase I; 12 Phase I providers will be recruited from Temple or other sites. In Years 2-5, we plan to enroll 256 Fox Chase patients, and 5-8 Fox Chase providers. Overall, a lower accrual goal is 305, a total target accrual goal is 339, and an upper accrual goal for Fox Chase is 349. We may also recruit Temple providers or other outside providers for Phase II if we are unable to recruit a sufficient number of internal clinicians for this phase of the study. If we are able to recruit a Temple or outside provider, then the number of target patients may change slightly for Fox Chase, because we will be recruiting about 16 patients per provider from outside Fox Chase.

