4.1.2. Recruitment and Reimbursement of Patient Participants

Across all study phases, a target of 315 patients will participate in the study: 30 participants in Phase I (Qualitative Study); 24 focus group participants, 6 mock training participants); 168 patients in Phase II (Provider Training Study); and 144 in Phase III (Patient Training Study); 24 patients in the exploratory focus groups, and 5 in the cognitive interviews.

Candidates for Phase I (qualitative study/mock training) and for the exploratory focus groups will be recruited primarily through advertisements both internally via clinics at Fox Chase/Temple and externally via established community partners and other sites, telephone, and in-person at clinic at Fox Chase or Temple after identification through providers' schedules, or after identification through the Fox Chase Cancer Registry, using a study introductory letter (see supplemental materials). For patients identified through the Registry, patient lists will be approved by the patients' physician prior to sending the introductory letter. Given an approximately 20% no-show rate for the qualitative focus groups, we will recruit and schedule between 5 to 8 patients for focus groups, assuming that several candidates will not

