4.3.2. Provider Training Study Design (Phase II)

A self-report survey will be given to providers participating in this phase to complete soon after consent (generally within one week). The table below shows the schedule of self-report measures to be completed by providers participating in the Provider Training program. At baseline (pre-training), providers will report socio-demographic information and rate self-efficacy and outcome expectancies for communicating about sexual concerns with their breast cancer patients,⁶⁷ reliable measures of beliefs associated with communication behaviors, and the extent to which they endorse certain barriers (e.g., time pressures, etc.) as limiting their communication with breast cancer patients about sexual concerns. The items assessing barriers are taken from a published study in which they showed sensitivity to change through participation in a provider training intervention.⁶⁸ Providers will complete the measures of self-efficacy and outcome expectancies at three other time points: immediately post-training, and 1- and 6-month follow-ups. Efforts will be made to collect data at all time points in person using paper and pencil questionnaires from provider participants, although telephone, web, or mail-based paper administration may also be conducted if necessary.

Provider Training (Phase II) Self-Report Measures To Be Completed by Providers				
Measure	Baseline	Post-Training	1-Month Follow-up	6-Month Follow-up
Demographics (6 items)	X	-	-	-
Beliefs ⁶⁷	X	X	X	X
- Self-efficacy (3 items)				
- Outcome expectations (7 items)				
- Barriers (14 items)				
Feasibility and Acceptability Items	-	X (19 items)	X (14 items)	X (14 items)
Future Program Preferences	-	-	-	X (8 items)

Patients participating in this phase of the study will complete a survey immediately after the clinic visit that includes a socio-demographic questionnaire (6 items), health-related quality of life (HRQOL) items (8 items), and several questions assessing the communication that occurred during their clinic visit, that, together, is expected to take no more than 5-10 minutes to complete. The HRQOL information captures information that will help us interpret the communication findings, while the communication items will supplement the audio recorded communication data or replace it, in cases in which we cannot obtain audio recordings of the dialogue.

Provider Training Primary Learning Targets

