13.2.4. Sample Size Calculations

Because the objective of the Provider Training Study (Phase II) is to pilot test the newly developed provider training intervention, we do not conduct sample size calculations for this phase of the study, with the sample of 6-8 providers chosen based on what is feasible to accomplish in a pilot. Instead, sample size justification is provided below for the Patient Training Study. We will calculate pre-post effect sizes to inform a larger R01 trial that is expected to follow from this study.

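### The optional Phase II GEE 95% intervals rest on 6-8 providers with no small-cluster method named; in standard uncorrected form they would be too short

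*Combined protocol and SAP*

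**What the plan says.** Section 13.2.3 (Phase II analyses) makes a descriptive comparison of proportions of visits the main look at clinician communication. It then adds "exploratory analyses on the communication variables where the effect of post-intervention was evaluated using generalized linear models with robust standard errors", using GEE to allow for correlation within provider. Binary behaviours get logistic regression, discussion length gets Poisson regression, and complexity and patient satisfaction get ordinal logistic regression. On reporting, the section says that although "the study was not powered for formal comparisons, we will consider presenting the model based estimates of effect sizes and corresponding 95% confidence intervals".

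Section 13.2.4 gives no sample size calculation for this phase, "with the sample of 6-8 providers chosen based on what is feasible to accomplish in a pilot". It adds: "We will calculate pre-post effect sizes to inform a larger R01 trial that is expected to follow from this study".

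On visit numbers, sections 4.1.1 and 4.3.2 aim for 8-16 visits per provider at baseline and about as many after training, but section 4.1.1 warns that "we may ultimately recruit fewer than 8 or more than 16 patients for some providers". Section 4.1.2 lists "168 patients in Phase II (Provider Training Study").

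No section names a small-sample variance correction, a t reference, a bootstrap or a permutation method for these intervals.

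**The concern.** The sandwich variance is justified as the number of clusters grows. The clusters here are providers, so the relevant sample size is 6-8, however many visits are recorded. With so few clusters the uncorrected sandwich variance is biased downward, and a normal critical value ignores the uncertainty in estimating that variance. Both errors shorten the interval.

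The statement that the phase is not powered does not cover this. An underpowered study should give wide intervals, whereas these would be too narrow. A reader would take an interval labelled 95% to be more precise than it is. The modelled behaviours, complexity and discussion length are Phase II primary outcomes in section 13.2.1, and GEE is the only planned analysis of them that allows for clustering.

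**Working it through.** **Inputs from the documents.** Number of providers K = 6 to 8 (13.2.4). Nominal level 95% (13.2.3). Visits per provider per period: 8-16 (4.3.2); the stated minimum of 48 baseline visits is 6 × 8. With 168 patients (4.1.2), visits per provider per period are 168/(2K) = 14, 12 and 10.5. The total of 315 in the same section implies 315 - 30 - 144 - 24 - 5 = 112 Phase II patients instead, or 9.3, 8 and 7 visits. Both counts were simulated.

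**Closed form.** Take a balanced contrast with one pre-post difference d_i per provider and sample variance s². The uncorrected sandwich variance of the mean difference is Σ(d_i - d̄)²/K² = (s²/K) × (K-1)/K. For normally distributed differences, the mean divided by s/√K follows t on K-1 df, so a 1.96 interval covers

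P(|t(K-1)| < 1.96 × √((K-1)/K)).

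| K | 1.96 × √((K-1)/K) | Coverage |
|---|---|---|
| 6 | 1.789 | 86.6% |
| 7 | 1.815 | 88.0% |
| 8 | 1.833 | 89.1% |

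The plan's 95% is approached by this formula only with many clusters (94.0% at K = 40). Partial corrections at K = 6 to 8: K/(K-1) scaling with a normal reference gives 89.3-90.9%; the uncorrected variance with t on K-1 df gives 93.4-93.7%; both together give 95.0%.

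**Simulation of the planned models.** The documents give no Phase II event rates or provider variances, so these are assumptions: provider SD 0.3-1.0 logits, SD of the training effect 0 or 0.5, independence working correlation.

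- Logistic, baseline 10-25% rising to 25-45%, even visits, 168 patients (20,000 runs per setting): 85.1-87.7% (K = 6), 86.8-88.8% (7), 88.1-90.1% (8). With 112 patients: 85.9-89.1%, 87.8-90.6%, 88.9-91.6%.
- A second set, baseline 15% or 30%, with or without a training effect whose SD was up to 1 logit (40,000 runs): 84.2-87.1% (K = 6), 87.2-89.5% (K = 8).
- Exchangeable working correlation (1,200 runs, so Monte Carlo error of about 1 point): 82.8-86.2% (K = 6), 89.1-89.4% (K = 8).
- Rarer behaviour, 5% rising to 15%, even visits: 86-92%, 88-94%, 89-94% for K = 6, 7, 8. At 2% rising to 10%, 11-37% of runs have no finite odds ratio, which no variance correction repairs.
- Ordinal complexity: 83.3-87.6% (K = 6), 86.3-90.0% (K = 8).
- Discussion length, Poisson, zeros plus lognormal seconds: 79.4-86.4% (K = 6), 82.9-89.5% (K = 8), depending on assumed skewness.

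**Uneven visits.** In the second logistic set, visits varying over 8-16 differed from a constant 12 by at most 0.7 points (for example 86.3% against 87.0% at K = 6). A much wider assumed spread of about 3-26 visits gave 83.7-86.7%, 85.4-87.7% and 86.3-89.1% for K = 6, 7, 8, up to about 2 points lower than even visits.

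**After correction (t on K-1 df).**

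| Outcome | K/(K-1) scaling | Mancl-DeRouen |
|---|---|---|
| Binary, even visits | 94.2-97.0% | 95.5-97.8% |
| Binary, 3-26 spread | 93.2-95.2% | 95.0-96.8% |
| Ordinal | 92.7-95.3% | not run |
| Discussion length | 90.1-95.3% | 92.4-96.5% |

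**Width cost.** t(0.975, K-1)/1.96 × √(K/(K-1)): 2.571/1.96 × √(6/5) = 1.44; 2.447/1.96 × √(7/6) = 1.35; 2.365/1.96 × √(8/7) = 1.29.

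**The case against.** The best defence is that the plan already limits these intervals. The models are exploratory, intervals are only to be considered for presentation, the phase is declared not powered, and the main communication comparison is descriptive. Naming the sandwich variant in a pilot plan may look like reviewer preference. This stands as a limit on severity, but it does not answer the coverage question.

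Four stronger readings are tempting and are not supported:

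- *The plan commits to a normal-based interval.* It does not; it is silent. The 86.6-89.1% figures belong to the uncorrected normal-reference interval in a balanced contrast and do not describe every outcome model.
- *Uneven visit numbers make matters materially worse.* Section 4.1.1 allows departures from 8-16 but gives no limits. Variation within 8-16 barely matters, and the 3-26 spread is an assumption.
- *The intervals will set the size of the later trial.* Section 13.2.4 refers to pre-post effect sizes, and section 13.2.3 defines one for self-report measures as mean difference over the SD of the differences, which is not a GEE output. It also mentions model-based effect sizes, so the reference is ambiguous, but no section says the intervals feed planning.
- *Refusal of recording will push the clusters below six.* Section 5.0 lets clinicians decline recording, but section 4.3.2 says "the communication items will supplement the audio recorded communication data or replace it", and section 4.1.1 says "We may also recruit Temple providers or other outside providers for Phase II". The number of providers may differ by measure; how far is not known.

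**Conclusion.** The point holds in conditional form and at the lowest severity. With 6-8 providers and no small-cluster method named, the standard form of the planned interval would miss the true value about 11-13% of the time in the balanced closed form (100 - 89.1 = 10.9; 100 - 86.6 = 13.4), against a nominal 5%. For binary behaviours at 10% or above, simulated coverage is about 85-90% with the listed 168 patients, and slightly higher at the top of the range with 112. It is usually nearer nominal for rarer behaviours and lower for discussion length.

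The closed form assumes equal clusters and normal provider differences. The simulations rest on assumed event rates, provider variances and skewness. Confidence in the arithmetic is high; which interval the investigators would use is unknown. Point estimates, enrolment and every decision rule are unaffected.

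**What to change.** For any Phase II GEE interval that is reported, use a small-sample-corrected sandwich variance (for example K/(K-1) scaling, or Mancl-DeRouen where the software offers it) with a t reference on (contributing providers - 1) df. State beside each interval how many providers contributed. Add a note that discussion-length and ordinal intervals may still cover somewhat below 95%. Mancl-DeRouen was not checked for the ordinal models and is slightly conservative for binary outcomes.

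The cost is one sentence and, for the binary and Poisson models, usually a software option; the ordinal models may need the scaling applied by hand. Intervals become 1.44, 1.35 or 1.29 times as wide for 6, 7 or 8 providers with K/(K-1) and t, and about 1.57, 1.46 or 1.38 times with Mancl-DeRouen and t. Section 4.3.3 shows that Phase II results already existed at this version, so this is a reporting choice and changes no conduct of the study.
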